9.2 Background Characteristics

9.2.1 Subject Disposition

The number of subjects in the following categories will be summarized:

- All Subjects Set/Enrolled
- Full Analysis Set (FAS)
- Safety Set
- Enrolled but not dosed

The number and percentage (based on the FAS) of subjects in each of the following disposition categories will be summarized:

- Completed treatment and the reason for completion of treatment
- Prematurely discontinued treatment and the reason for discontinuation from treatment
- Completed study
- Prematurely discontinued the study and the reason for discontinuation from study

A disposition listing of subjects will be provided.

9.2.2 Demographics and Baseline Characteristics

Demographics and baseline characteristics will be summarized based on the FAS.

Demographic data will include the following:

- Age at screening (in years)
- Age at screening category (≥ 18 to <65, ≥ 65 years)
- Sex (male, female)
- Ethnicity (Hispanic or Latino, not Hispanic or Latino, and not collected per local regulations)

• Race (White, Black or African American, Asian, American Indian or Alaska Native, Native Hawaiian or Other Pacific Islander, not collected per local regulations, Other, and Multiracial [if 2 or more races reported from a subject])

Baseline characteristics will include the following:

- Weight (kg)
- Height (cm)
- BMI (kg/m^2)
- NPRS
- NPRS category ($< 8, \ge 8$)
- VRS (moderate, severe)
- Surgical/non-surgical status
- Surgery type
- Site

In addition to demographic data and baseline characteristics, data listings will also be provided for:

- Informed consent
- Inclusion/exclusion criteria violation for subjects with any such violations

9.2.3 Medical History

Medical history will be coded using the Medical Dictionary for Regulatory Activities (MedDRA). Medical history will be summarized descriptively based on the FAS by MedDRA system organ class (SOC) and preferred term (PT). The corresponding data listing will also be provided.

9.2.4 Prior and Concomitant Medications

Medications will be coded using the World Health Organization Drug Dictionary and categorized as the following for the purpose of analysis:

Prior medication: Medication that started before the first dose of study drug, regardless of when dosing of the medication ended

Concomitant medication: Medication continued or newly received after the date and time of the first dose of study drug through the end of the TE Period

A given medication may be classified as a prior medication, a concomitant medication, or both a prior and a concomitant medication.

If a medication start date/time is on or after the first dose of study drug, then the medication will be classified as a concomitant medication regardless of whether the medication end date/time is missing. If a medication end date/time is before the first dose of study drug, then

the medication will be classified as a prior medication regardless of whether the medication start date/time is missing.

Note that a medication that started before the first dose of study drug and continued after the first dose will be classified as a prior medication and separately as a concomitant medication. If a medication has a missing or partially missing start or end date/time and it cannot be determined whether it was taken before the first dose of study drug or concomitantly, it will be classified as a prior and a concomitant medication.

Details for imputing missing or partial start/end date and time of medication are described in Appendix B.

Prior and concomitant medications will be summarized based on the FAS by Preferred Name and listed. Pre- and intra-operative medications and supplemental analgesic medications for surgical subjects will be included in the summary of prior medications. Rescue medication taken prior to the subject's last dose of VX-548 will be included in the summary of concomitant medications. The proportion of subjects taking any rescue medication will be summarized separately. In addition, for acetaminophen and ibuprofen separately, the mean dose administered per day of VX-548 exposure (calculated for each subject as the total dose / number of days of exposure) will be summarized.

Prior and concomitant non-pharmacological treatments or procedures will also be listed.

9.2.5 Study Drug Exposure and Study Drug Compliance

Study drug exposure (in days) will be calculated as (last date of dosing – first date of dosing) + 1. This will be summarized overall, as well as for those who completed treatment and for those who discontinued treatment. Study drug exposure will also be summarized in categories: ≤ 3 days, >3 to ≤ 7 days, and >7 days, using counts and percentages.

Compliance will not be analyzed due to the complex nature of starting and stopping the study drug as explained in Section 9.1 of the CSP.

All data collected during dispensation of study drug (e.g., time of administration and number of tablets taken) will be presented in an individual data listing.

9.2.6 Important Protocol Deviations

An important protocol deviation (IPD) is a deviation that may significantly affect the completeness, accuracy, or reliability of the study data or that may significantly affect a subject's rights, safety, or well-being. IPD rules will be developed and finalized before database lock. IPDs will be identified by the PD review team according to the protocol deviation plan.

IPDs will be summarized descriptively and presented in an individual data listing.

9.3 Effectiveness Analysis

The secondary endpoint is the subject perception of VX-548 effectiveness in treating pain at the end of treatment as measured by the proportion of subjects reporting good, very good, or excellent on a patient global assessment (PGA). The PGA of study drug is a single-item assessment of patient perceptions of the method of pain control with the study drug and will be evaluated on a 5-point Likert scale (poor, fair, good, very good, or excellent). The

proportion of subjects reporting good, very good, or excellent, at the end of treatment will be presented descriptively based on the FAS, as well as the proportion of subjects providing each response. The PGA at the end of treatment is defined as either the PGA collected on Day 14 or the PGA associated with the End of Dosing Visit for subjects who complete or discontinue study drug treatment before Day 14. Missing PGA assessments at the end of treatment will be imputed using the previous PGA assessment. Subjects with no previous PGA assessments available will be considered non-responders and will be included in the denominator when calculating the proportions.

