PGA		X			X	X	X		Recorded in the e-diary ^d ; Section 11.4.1. Subjects should still complete the PGA even if the specified dose is not taken. Day 2: To be completed after the third study drug dose (approximately 24 hours after the first dose). Day 7: Completed after the first study drug dose on Study Day 7 (whether or not this coincides with the date of the Day 7 Visit). Day 14 or EDV: Completed after final study drug dose for subjects still taking study drug on Day 14. Subjects who have discontinued or completed study drug treatment should complete the PGA at home within approximately 24 hours after the last (or presumed last) dose of study drug rather than waiting for their scheduled visit.
Vital signs			X (postdose) ^b		Х	х	Х	Х	Vital signs will be collected after a \geq 5-minute rest (seated or supine) and before any 12-lead ECG assessment or blood sampling; Section 11.5.3.
Standard 12-lead ECG	at discharg	ours after first e or before lea ility, as applic	ving medical		X (4 hours after a dose) ^e	X (4 hours after a dose) ^{e,f}	X	(X)	Required at SFU only if any clinically significant abnormalities were noted on a prior ECG. Standard 12-lead ECGs will be performed in triplicate after a ≥5-minute rest (supine); these will be done after taking vital signs and before any procedures that may affect heart rate (e.g., blood sampling); Section 11.5.4.

Table 3-4Study VX22-548-107: Treatment Period and Safety Follow-up Visit (All Subjects)

Table 3-4Study VX22-548-107: Treatment Period and Safety Follow-up Visit (All Subjects)

Event/Assessment ^a	Day 1	Day 2	Discharge ^b	Day 4 (± 1 day)	Day 7 (± 1 day)	Day 14 (+ 3 days)	End of Dosing Visit ^c	Safety Follow-up Visit Day 28 (± 2 days)	Comments
Symptom-directed PE				As applicable					Symptom-directed PEs will occur at any time during the study if triggered by AEs or if deemed necessary by the investigator; Section 11.5.3.
Focused PE (surgical subjects only)								Х	Assessment of wound healing at the operative site; Section 11.5.3.
Complete PE								(X)	Required at SFU only if a clinical finding during the Treatment Period requires follow up, in which case the subject must have a clinic visit; Section 11.5.3.
C-SSRS			X (postdose) ^b		Х	Х	X		Section 11.5.5
Urine β-hCG						Х	Х	Х	All female subjects of childbearing potential; Section 11.5.2.
Serum chemistry			X (postdose) ^b			Х	X	(X)	Required at SFU only if a clinical finding during the Treatment

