7.2 Secondary Endpoint

Subject perception of VX-548 effectiveness in treating pain at the end of treatment as measured by the proportion of subjects reporting good, very good, or excellent on a patient global assessment (PGA)

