9 STATISTICAL ANALYSIS

9.1 General Considerations

The Schedule of Assessments is provided in Section 3 of the CSP. The precision standards for reporting variables are provided in an internal Biometrics document that specifies the programming rules including the precision for derived variables.

All individual subject data for subjects who have received at least 1 dose of study drug will be presented in individual subject data listings.

Continuous variables will be summarized using the following descriptive summary statistics: the number of subjects (n), mean, standard deviation (SD), median, minimum value (min), and maximum value (max).

Categorical variables will be summarized using counts and percentages.

Baseline value, unless specified otherwise, will be defined as the most recent non-missing measurement (scheduled or unscheduled) collected before the first dose of study drug.

For ECGs, the baseline value will be defined as the average of the most recent non-missing measurements (scheduled or unscheduled) collected before the first dose of study drug, expected to be the triplicate predose measurements on Day 1.

Change (absolute change) from baseline will be calculated as post-baseline value – baseline value.

Treatment-emergent (TE) Period will include the time from the first dose of study drug to the Safety Follow-up Visit or to the completion of study participation (as defined in Section 9.1.7 of the CSP), whichever occurs first.

Unscheduled visits: Unscheduled visit measurements will be included in the analysis as follows:

• In scheduled visit windows per specified visit windowing rules

- In the derivation of baseline
- In the derivation of maximum and minimum values during the TE period, and maximum and minimum change from baseline values during the TE period for safety analyses
- In individual subject data listings as appropriate

Visit windowing rules: The analysis visit windows for protocol-defined PGA entries, which are provided by the subject in a dosing diary, are provided in Appendix A. All safety assessments are analyzed according to their nominal visits.

Outliers: No formal statistical analyses will be performed to detect and/or remedy the presence of statistical outliers.

Multiplicity: Only descriptive analyses will be performed; no statistical hypothesis testing will be performed.

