12 LIST OF APPENDICES

Appendix A: Analysis Visit Windows for Effectiveness Assessments

Table 12-1 Analysis Visit Windows for Effectiveness Assessments			
Assessment	Visit/Timepoint	Target Study Day	Analysis Visit Window (in study days/timepoints)
PGA	EDV	After treatment completion/disconti nuation	First assessment between 0 and 48 hours after subject's last dose of VX-548

Note: If no PGA measurement is available within the EDV visit window, PGA at EDV will be imputed with the previous PGA measurement, if available.

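### Does SAP 9.3 need Day 2 and Day 7 PGA summaries, a split by stopping status and a confidence interval?

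*SAP*

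**What the plan says.** **Endpoint.** Protocol 7.2 defines the secondary endpoint as "Subject perception of VX-548 effectiveness in treating pain at the end of treatment", measured by the proportion rating the drug good or better. SAP 6.2 repeats it.

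**Collection.** The PGA row of Protocol Table 3-4 has two ratings before the final one: "Day 2: To be completed after the third study drug dose (approximately 24 hours after the first dose") and "Day 7: Completed after the first study drug dose on Study Day 7". The final rating follows the last dose on Day 14 or, for subjects who stop earlier, is made at home within about 24 hours of the last dose.

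**Analysis.** SAP 9.3 states that the "proportion of subjects reporting good, very good, or excellent, at the end of treatment will be presented descriptively based on the FAS", together with the proportion giving each response. It defines the end-of-treatment rating as follows: "PGA collected on Day 14 or the PGA associated with the End of Dosing Visit for subjects who complete or discontinue study drug treatment", where the second case means stopping ahead of Day 14. On missing values it says: "Missing PGA assessments at the end of treatment will be imputed using the previous PGA assessment". Subjects with no earlier rating count as non-responders and stay in the denominator.

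**Windows.** SAP 9.1 says: "The analysis visit windows for protocol-defined PGA entries, which are provided by the subject in a dosing diary, are provided in Appendix A". Table 12-1 in that appendix has one row, for the End of Dosing Visit: "First assessment between 0 and 48 hours after subject's last dose of VX-548".

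**Style of analysis.** SAP 9.1 plans counts and percentages for categorical data, individual listings for every dosed subject, and no hypothesis tests.

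**The concern.** Two of the three scheduled PGA time points have no planned table. Their only stated analytic use is to fill in a missing final rating.

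The final rating has no common clock time, and it pools three kinds of subject: those still on drug at Day 14, those who completed early because pain resolved, and those who discontinued. Disposition (SAP 9.2.1) and exposure (SAP 9.2.5) are tabulated, but neither is crossed with the PGA. No count of carried-forward ratings and no interval is planned. Protocol 9.3.1 says the study is designed to look at sustained effect, and one rating per subject at a subject-specific time does not describe a course over treatment.

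If this were a defect, readers could take one pooled percentage for evidence of lasting benefit. Time points could also be chosen for display after the data are seen.

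**Working it through.** **1. The plan's own figure.** The sample size rests on adverse-event detection (SAP 7.1), with nothing for the PGA. P(at least 1 event) = 1 − (1 − p)^250. For p = 0.01 this is 0.9189 (stated 92%). For p = 0.02 it is 0.9936 (stated 99%). Both reproduce, and the PGA has no precision target to miss.

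**2. Spread of rating times.** Assume exact 12-hourly dosing and a first dose at clock hour t on Day 1. Day 14 then runs from 312 − t to 336 − t hours after the first dose.
- First dose before noon: dosing slots at 312 and 324 h.
- First dose at noon or later: slots at 300 and 312 h.

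The single Day 14 dose therefore falls between 300 and 324 h, and the earliest possible last dose is at 0 h. The permitted dosing windows widen this a little. The spread is real, but it comes from an end-of-treatment endpoint in a study where treatment ends when pain resolves. It is not an error in the analysis.

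**3. Which ratings need a window.** Table 12-1 counts from the last dose. The Day 14 rating is made after the last dose, and an early stopper's rating is asked for within about 24 hours of it, so a rating made on schedule falls within 0 to 48 hours in both cases. Carry-forward needs only the order of ratings. No planned output uses a Day 2 or Day 7 window, so the missing rows change nothing that will be computed.

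**4. The missing interval.** SAP 9.3 will report the count x on a known denominator n. The exact 95% limits are the 0.025 quantile of Beta(x, n − x + 1) and the 0.975 quantile of Beta(x + 1, n − x). The documents give no expected rate, so these results are assumed:

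| x/n | Rate | Exact 95% limits |
|---|---|---|
| 125/250 | 50% | 43.6% to 56.4% |
| 200/250 | 80% | 74.5% to 84.8% |
| 225/250 | 90% | 85.6% to 93.4% |
| 20/25 | 80% | 59.3% to 93.2% |

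The last row is a non-surgical subgroup at the 10% threshold of SAP 9.5 (0.10 × 250 = 25). Anyone holding the report can compute these limits.

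**5. Pooling over stopping status.** With a share d discontinuing, and assumed responder rates of 90% in completers and 30% in discontinuers, the pooled rate is 0.9(1 − d) + 0.3d. For d = 5%, 10%, 20% and 30% this gives 87%, 84%, 78% and 72%. Each is the quantity the endpoint asks for: responders among all treated subjects, whatever their reason for stopping. A split would explain the figure but not correct it.

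**6. What the extra tables could show.**
- *Day 7.* Subjects who have stopped rate the drug within about a day of their last dose, and an early End of Dosing Visit removes the Day 7 Visit. Day 7 ratings would come mainly from subjects still dosing, whose pain has not resolved. A sequence from Day 2 to Day 7 to end of treatment would compare different groups of people.
- *Stopping status.* Early completion largely means that pain resolved (Protocol 9.1), so better ratings among completers are close to built in. At 25 non-surgical subjects, three groups average about 8 each (25/3).
- *Windows.* A calendar-day window for Day 2 would miss compliant entries. Doses at 22:30 on Day 1, 11:30 on Day 2 and 00:30 on Day 3 are each 13 hours apart, within the limit of 12 ± 1 hours, yet the third dose falls on Day 3.
- *Counts.* A subject whose last dose is on Day 6 and who rates on Day 7 is both off drug and observed at Day 7. The groups overlap unless a precedence rule is written.

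**The case for a change.** The strongest case for a change is that Protocol 12.3.3 promises a descriptive PGA summary without limiting it to end of treatment, and leaves the detail to the SAP. The data are already collected, and the completed/discontinued split already exists for exposure. A few descriptive tables would cost little, and naming them before database lock would prevent selective display. An interval needs no hypothesis test, and it would show how weak a subgroup of 25 is.

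Part of this stands. The omissions are real, and the cross-reference in SAP 9.1 promises more than Table 12-1 holds. A count of carried-forward ratings would help a reader, although it can be compiled from the listings.

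The rest does not make the plan deficient. Sustained effect is mentioned in the design rationale and is neither an objective nor an endpoint. The same section says the study is mainly for safety information. The endpoint and its time point are already fixed, so later display of Day 2 or Day 7 ratings could not replace the secondary result. With no control arm and no tests, the extra tables would also not show whether the drug's effect lasts.

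**Conclusion.** No change is needed. SAP 9.3 delivers the secondary endpoint as Protocol 7.2 defines it, with a stated denominator, a full response distribution and a rule for missing ratings. The effect of the omissions on any planned number is zero, and the primary safety analysis is untouched.

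The unmatched reference from SAP 9.1 to Appendix A is a clerical slip. The interval can be computed from the reported counts, at roughly 4 to 6 percentage points either side for 250 subjects with rates between 90% and 50%. The Day 2 and Day 7 tables and the split by stopping status are optional reporting, and selection and overlapping groups limit what they could show.

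This rests on three things: the endpoint stays at end of treatment, the report gives counts with the full analysis set as denominator, and the individual ratings are listed as SAP 9.1 plans. The response and discontinuation rates used above are assumptions, and the conclusion does not depend on them. If the study report were to claim a sustained effect, the end-of-treatment proportion would not support that claim, but the plan makes no such claim for it.

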9.4 Safety Analysis

The following safety and tolerability assessments will be used to evaluate the overall safety profile of VX-548:

- Incidence of treatment-emergent adverse events (TEAEs)
- Clinical laboratory values (hematology, serum chemistry, coagulation, and urinalysis)
- ECG outcomes
- Vital signs
- Columbia-Suicide Severity Rating Scale (C-SSRS)

All safety analyses will be performed based on the Safety Set.

9.4.1 Adverse Events

AEs will be coded according to MedDRA. For analysis purposes, AEs will be classified as pretreatment AEs and TEAEs as follows:

Pretreatment AEs: AEs that occurred before the first dose of study drug

Treatment-emergent AEs: AEs that worsened or started after the first dose of study drug through the end of the TE Period

For AEs with completely missing or partial start dates/times, if there is no clear evidence that the AEs started before or after the first dose of study drug, the AEs will be classified as TEAEs.

Imputation rules for missing or partial AE start dates/times are defined in Appendix C.

AE summary tables will be presented only for TEAEs, and will include the following:

- All TEAEs
- TEAEs by strongest relationship
- TEAEs by maximum severity
- TEAEs leading to treatment discontinuation
- TEAEs leading to treatment interruption
- Related TEAEs
- Serious TEAEs

- Related serious TEAEs
- TEAEs leading to death

Summaries will be presented by MedDRA SOC and PT using frequency counts and percentages (i.e., number and percentage of subjects with an event). When summarizing the number and percentage of subjects with an event, subjects with multiple occurrences of the same AE or a continuing AE will be counted once, and only the maximum severity level will be presented in the severity summaries, and the strongest relationship level in the relationship summaries.

All AEs, including pretreatment AEs and TEAEs, will be presented in an individual subject data listing. In addition, a listing containing individual subject AE data for TEAEs leading to treatment discontinuation, TEAEs leading to treatment interruption, SAEs, and all deaths will be provided separately.

9.4.2 Clinical Laboratory Assessments

All statistical analyses of laboratory values will be performed using SI units. For treatmentemergent laboratory measurements, the observed values and change from baseline values of the continuous hematology, chemistry, and coagulation results will be summarized at each visit.

The number and percentage of subjects with selected test values meeting threshold analysis criteria during the TE period will be summarized. The number and percentage of subjects with shift from baseline in selected test values meeting threshold analysis criteria will also be summarized for chemistry measurements. The threshold analysis criteria are provided in Appendix D.

Results of urinalysis and the urine/serum pregnancy test will be in individual subject data listings only.

In addition, listings of individual subject hematology, chemistry, and coagulation values outside the normal reference ranges will be provided. These listings will include data from both scheduled and unscheduled visits.

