- 9. Any other abnormal laboratory results indicative of significant medical disease that, in the opinion of the investigator, would preclude the subject's participation in the study.
- 10. History of any sensory abnormality that, in the opinion of the investigator, may confound the ability of the subject to assess pain.
- 11. Subjects who have a painful physical condition that, in the opinion of the investigator, may confound the assessments of pain.

- 12. A known or clinically suspected active infection with human immunodeficiency virus or hepatitis B or C viruses. (**Note:** Testing in the absence of suspected active infection is required for surgical subjects only.)
- 13. Any surgery (except the protocol surgery for surgical subjects) within 1 month before the first study drug dose, unless approved by the medical monitor.
- 14. American Society of Anesthesiologists physical status classification²⁶ of \geq 3.
- 15. Chronic use of opioids (pure agonists, agonist/antagonists, partial agonists, antagonists) or NSAIDs with dose escalation within 30 days before first dose of study drug.
- 16. Unwilling or unable to stop analgesics at least 5 half-lives or 2 days (whichever is longer) before first dose of study drug, with the following exception: for non-surgical subjects, use of a limited amount of pain medications before presentation at the medical facility and/or single use of any medication in the medical facility within the past 4 hours is not exclusionary.
- 17. Subjects who have started any non-analgesic new medications that have not been at a stable dose for at least 14 days before first dose of study drug.
- 18. Subjects unwilling to receive any protocol-related medicine (e.g., ibuprofen, acetaminophen, fentanyl).
- 19. Subjects with a history of allergy or significant adverse event (AE) to any opioid and/or NSAID that, in the opinion of the investigator, would significantly increase the chance of AEs from medicines used in the study.
- 20. Subjects with sleep apnea and/or on a home positive airway pressure device.
- 21. History of peptic ulcer disease or gastrointestinal bleeding that, in the opinion of the investigator or medical monitor, would preclude the subject's participation in the study.
- 22. For female subjects: Pregnant, nursing, or planning to become pregnant during the study or within 30 days after the last study drug dose.

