Appendix D: Threshold Value Criteria

Parameter	Threshold Analysis	Comments
Clinical Chemistry		
ALT	>ULN - ≤3xULN >3x - ≤5xULN >5x - ≤8xULN >8x - ≤20xULN >20xULN	FDA DILI Guidance Jul 2009.
AST	>ULN - ≤3xULN >3x - ≤5xULN >5x - ≤8xULN >8x - ≤20xULN >20xULN	FDA DILI Guidance Jul 2009.
ALT or AST	$\begin{array}{l} (ALT>ULN - \leq 3xULN) \text{ or } (AST>ULN - \\ \leq 3xULN) \\ (ALT>3x - \leq 5xULN) \text{ or } (AST>3x - \\ \leq 5xULN) \\ (ALT>5x - \leq 8xULN) \text{ or } (AST>5x - \\ \leq 8xULN) \\ (ALT>8x - \leq 20xULN) \text{ or } (AST>8x - \\ \leq 20xULN) \\ ALT>20xULN \text{ or } AST>20xULN \end{array}$	- FDA DILI Guidance Jul 2009.
Alkaline Phosphatase	>ULN - ≤1.5xULN >1.5 - ≤2.5xULN >2.5 - ≤5xULN >5 - ≤20xULN >20xULN	FDA DILI Guidance Jul 2009.
Total Bilirubin	>ULN - ≤1.5xULN >1.5 - ≤2xULN >2 - ≤3xULN >3 - ≤10xULN >10xULN	FDA DILI Guidance Jul 2009.
Direct Bilirubin	>ULN - ≤1.5xULN >1.5 - ≤2xULN >2 - ≤3xULN >3 - ≤10xULN >10xULN	FDA DILI Guidance Jul 2009.
ALT and Total Bilirubin	ALT>3xULN and TBILI>2xULN	FDA DILI Guidance Jul 2009.
AST and Total Bilirubin	AST>3xULN and TBILI>2xULN	FDA DILI Guidance Jul 2009.
(ALT or AST) and Total Bilirubin	(ALT>3xULN or AST>3xULN) and TBILI>2×ULN	FDA DILI Guidance Jul 2009.

Parameter	Threshold Analysis	Comments
GGT	>ULN - ≤2.5xULN >2.5 - ≤5xULN >5 - ≤20xULN >20xULN	CTCAE grade 1-4
Albumin	<lln -="" g="" l
<30 - ≥20 g/L <20 g/L</lln>	CTCAE grade 1-3
Creatinine	>ULN - ≤1.5xULN >1.5 - ≤3xULN >3 - ≤6xULN >6xULN	CTCAE grades 1-4
Lipase	>ULN - ≤1.5xULN >1.5x - ≤2xULN >2x - ≤5xULN >5xULN	Criteria based upon CTCAE
Total protein	<lln >ULN</lln 	No CTCAE
Creatine kinase	>ULN - ≤2.5xULN >2.5 - ≤5xULN >5 - ≤10xULN >10xULN	CTCAE grades 1-4
Hematology		
Hemoglobin	Hgb decreased (anemia) <lln -="" g="" l
<100 - ≥80 g/L <80 g/L</lln>	CTCAE grade 1-3
	Hgb increased >ULN - ≤20 g/L above ULN >20 g/L above ULN - ≤40 g/L above ULN >40 g/L above ULN	CTCAE grade 1-3
Platelets	Platelet decreased <lln -="" 10e9="" l
<75.0 - ≥50.0 x 10e9 /L <50.0 - ≥25.0 x 10e9 /L <25.0 x 10e9 /L</lln>	CTCAE grade 1-4
	Platelet increased >ULN	No CTCAE available
Coagulation		
Activated partial thromboplastin time (PTT)	>ULN - ≤1.5xULN >1.5 - ≤2.5xULN >2.5xULN	CTCAE grade 1-3

Table 12-3 Threshold Analysis Criteria for Laboratory Tests (as applicable)

Parameter	Threshold Analysis	Comments
Prothrombin time (PT)	>ULN - ≤1.5xULN	CTCAE grade 1-3
International	>1.5 - ≤2.5xULN	
Normalized Ratio (INR)	>2.5 x ULN	

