Table 12-3 Threshold Analysis Criteria for Laboratory Tests (as applicable)

Table 12-4 Threshold Analysis Criteria for ECGs

Parameter	Threshold Analysis	Comments
HR	Bradycardia <50 bpm <45 bpm Decrease from baseline ≥10 bpm Decrease from baseline ≥20 bpm <50 bpm and decrease from baseline ≥10 bpm <50 bpm and decrease from baseline ≥20 bpm	Per HV grade 2, 3, plus shift change
	Tachycardia >100 bpm >115 bpm >130 bpm Increase from baseline ≥10 bpm Increase from baseline ≥20 bpm >100 bpm and increase from baseline ≥10 bpm >100 bpm and increase from baseline ≥20 bpm	Per HV grade 1, 2, 3, plus shift change
PR	≥240 ms ≥300 ms ≥200 ms and increase from baseline ≥40 ms ≥200 ms and increase from baseline ≥100 ms	
QRS	>110 ms >160 ms Increase from baseline ≥20 ms Increase from baseline ≥40 ms	
QTc	>450 to <500ms (Male) or >470 to <500ms (Fema ≥500 ms Increase from baseline Increase from baseline >10 ms Increase from baseline >20 ms Increase from baseline >40 ms Increase from baseline >60 ms	ale) To be applied to any kind of QT correction formula.

Parameter	Threshold Analysis	Comments
Pulse Rate	Same as above in ECG category	
SBP increased	>140 mmHg	
	>160 mmHg	
	>10 mmHg increase from baseline	
	>20 mmHg increase from baseline	
	>140 mmHg & >10 mmHg increase from baseline	
	>140 mmHg & >20 mmHg increase from baseline	
	>160 mmHg & >10 mmHg increase from baseline	
	>160 mmHg & >20 mmHg increase from baseline	
SBP decrease	<90 mmHg	Per HV grade 1, 3, plus shift change
	<80 mmHg	
	>10 mmHg decrease from baseline	
	>20 mmHg decrease from baseline	
	<90 mmHg and >10 mmHg decrease from baseline	
	<90 mmHg and >20 mmHg decrease from baseline	
	<80 mmHg and >10 mmHg decrease from baseline	
	<80 mmHg and >20 mmHg decrease from baseline	
DBP increased	>90 mmHg	
	>100 mmHg	
	>5 mmHg increase from baseline	
	>10 mmHg increase from baseline	
	>90 mmHg and >5 mmHg increase from baseline	
	>90 mmHg and >10 mmHg increase from baseline	
	>100 mmHg and >5 mmHg increase from baseline	
	>100 mmHg and >10 mmHg increase from baseline	
DBP decreased	<60 mmHg	
	<45 mmHg	
	>5 mmHg decrease from baseline	
	>10 mmHg decrease from baseline	
	<60 mmHg and >5 mmHg decrease from baseline	
	<60 mmHg and >10 mmHg decrease from baseline	
	<45 mmHg and >5 mmHg decrease from baseline	
	<45 mmHg and >10 mmHg decrease from baseline	
Oxygen saturation	<88%	
decreased	<95% and decrease from baseline $>5%$ of absolute	
	oxygen saturation	

 Table 12-5
 Threshold Analysis Criteria for Vital Signs

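### Hematology and coagulation threshold counts mix abnormalities present at baseline with new or worsened ones, because the SAP plans shift summaries for chemistry only

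*SAP*

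**What the plan says.** SAP 9.4.2 plans these laboratory outputs:

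- By-visit summaries of observed values and change from baseline for hematology, chemistry and coagulation.
- A threshold count: "The number and percentage of subjects with selected test values meeting threshold analysis criteria during the TE period will be summarized". It sets no condition on the baseline value.
- A shift summary for one panel only: "shift from baseline in selected test values meeting threshold analysis criteria will also be summarized for chemistry measurements".
- Listings of hematology, chemistry and coagulation values outside the reference range.

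In Appendix D, Table 12-3, the hematology and coagulation criteria are levels against a limit. Examples are "Hgb increased >ULN - ≤20 g/L above ULN", "Platelet increased >ULN" and, for PTT, ">1.5 - ≤2.5xULN >2.5xULN". None includes a change from baseline. SAP 9.1 defines the TE period by time alone, from first dose to the Safety Follow-up Visit or end of participation.

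Protocol 8.2 sets numeric limits for ALT/AST and eGFR. Other laboratory results exclude a subject only under Exclusion 9: "Any other abnormal laboratory results indicative of significant medical disease", as the investigator judges it.

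**The concern.** Laboratory results are part of the primary endpoint, and the study has no control arm to show the background rate. A count of subjects beyond a limit during treatment is informative only if the reader can tell how many were already there before the first dose. For chemistry the shift summary answers that. For hematology and coagulation no planned laboratory table does.

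The panel is not incidental. Protocol 5.1 names hematologic toxicity as a risk of acute NSAID use, and ibuprofen is part of the rescue medication in Protocol 9.4.1.2.

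**Working it through.** **1. The plan's own figure.** SAP 7.1 gives the probability of at least one event among 250 subjects. The formula is 1 − (1 − p)^250.

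- p = 0.01: 0.9189 (stated 92%).
- p = 0.02: 0.9936 (stated 99%).

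Both reproduce and neither is in dispute. They concern adverse events, but they set a scale: at 1% incidence the expected number of subjects is 0.01 × 250 = 2.5.

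**2. How each domain treats a value already abnormal at baseline.**

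- Chemistry (SAP 9.4.2, Table 12-3): level rows plus a shift summary. Baseline and new cases can be separated.
- Heart rate and PR (Table 12-4), blood pressure and oxygen saturation (Table 12-5): level rows plus rows that join level and change, such as "<50 bpm and decrease from baseline ≥10 bpm".
- Hemoglobin, platelets, PTT and PT/INR (Table 12-3): level rows only and no shift summary. Baseline and new cases cannot be separated in a table.

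Take a subject with hemoglobin slightly below the lower limit at baseline and the same value on treatment. Exclusion 9 does not bar this subject unless the investigator sees significant disease. The on-treatment value meets the mildest anemia criterion, so the subject is counted, and nothing beside the count shows that nothing changed.

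**3. Illustrative size.** The documents give no baseline abnormality rate, so every rate here is assumed. Let b be the share beyond a given one-sided limit at baseline, r the share of those still beyond it on treatment, and i the new-onset rate among the rest.

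- Carried over from baseline = 250 × b × r.
- New = 250 × (1 − b) × i.

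With a central 95% reference range, b = 0.025:

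- At baseline: 250 × 0.025 = 6.25, about 6 subjects per one-sided limit.
- Carried over at r = 0.8 to 1.0: 5.0 to 6.25.
- New at i = 0.02: 250 × 0.975 × 0.02 = 4.9.
- Planned count: 9.9 to 11.1, of which 51% to 56% was present at baseline.

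Other assumed values of b, with r = 0.8 to 1.0, give these carried-over counts:

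- b = 0.02: 4 to 5.
- b = 0.05: 10 to 12.5.
- b = 0.10: 20 to 25.
- b = 0.20: 40 to 50.

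The range shows how far the answer depends on b. It is not an estimate for this trial.

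**4. What baseline means here.** SAP 9.1 takes the last value before the first dose. For surgical subjects, Protocol Table 3-1 schedules hematology and coagulation at screening (Day -28 to Day -1), and neither its Day 1 pre-procedure column nor Table 3-2 schedules a repeat. The next scheduled sample is the postdose one at discharge (Table 3-4). Surgery therefore falls between the scheduled baseline and the first on-treatment value.

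**The case against.** The strongest reply is that worsening is already counted elsewhere. Protocol 13.1.1.2 makes clinically significant worsening of a laboratory result an adverse event and uses anemia and low hemoglobin as examples. SAP 9.4.1 tabulates events that started or worsened after the first dose, by preferred term and by maximum severity. This stands. A reader might infer that the threshold table is the only categorical hematology and coagulation output, and that would be wrong. What is missing is a count that does not depend on the investigator's judgment of significance.

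A reader might also infer that the SAP reports pre-existing abnormalities as treatment-emergent. The documents do not support that. The threshold counts are described as values falling within a time window, and no row is named a treatment-emergent abnormality.

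Nor does the point carry over to QRS. Table 12-4 has separate QRS rows for increases of at least 20 and at least 40 ms, which a stable wide QRS does not enter.

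By-visit change summaries and out-of-range listings help, and 250 subjects can be reviewed one by one. But group statistics do not count new cases, and a listing leaves the counting to the reader. SAP 9.1 mentions deriving maximum and minimum change from baseline, but SAP 9.4.2 plans no laboratory table that uses them.

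Two further limits stand. Severe abnormalities at baseline are unlikely given Exclusions 3, 9 and 14 and the screening rule in Protocol 11.5.2, so the mixing falls mainly in the mildest category. And a shift table cannot separate drug effects from surgical ones in surgical subjects.

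**Conclusion.** The point holds as a limited one. The hematology and coagulation threshold counts combine abnormalities present at baseline with new or worsened ones. Apart from investigator-judged adverse events, no planned table counts subjects who moved to a worse category than at baseline. This follows from SAP 9.4.2 and Table 12-3 and does not depend on any assumed rate.

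The size does depend on assumption. About 6 of 250 subjects per one-sided limit follows from a central 95% reference range, and all 6 stay in the count only if every one of them remains beyond the limit. No test, sample size or decision rule is affected, because the study is descriptive. It is a cheap improvement to the reading of part of the primary endpoint. Shifts in surgical subjects will remain confounded with surgery.

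**What to change.** In SAP 9.4.2, extend the scope of the shift sentence from chemistry alone to chemistry, hematology and coagulation. Keep the existing threshold counts.

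Add a note to the new tables: for surgical subjects the scheduled baseline is the pre-surgical screening sample, so a shift includes perioperative effects such as blood loss and should not be read as a drug effect alone.

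No change to the QRS rows is needed. The cost is one amended sentence, one note and a few more tables from an analysis already planned for chemistry, repeated for the subgroups in SAP 9.5. Baseline is already defined and the samples are already scheduled, so there is no new data collection and no burden on subjects.
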